9.2 Reporting of Adverse Events

9.2.1 Reporting Procedures for Adverse Events That do not Meet Serious Criteria

The investigator is responsible for ensuring that all adverse events observed by the investigator or reported by the subject that occur after randomization through the safety follow-up visit (ie, 30 [+15] days after surgery) are reported using the applicable CRF (eg, Adverse Event Summary).

The investigator must assign the following adverse event attributes:

- Adverse event diagnosis or syndrome(s), if known (if not known, signs or symptoms),
- Dates of onset and resolution (if resolved),
- Severity [and/or toxicity per protocol],
- Assessment of relatedness to talimogene laherparepvec or surgery, and
- Action taken.

The adverse event grading scale used will be the CTCAE version 3.0. The grading scale used in this study is described in [Appendix A](#). The investigator must assess whether the adverse event is possibly related to talimogene laherparepvec or surgery. This relationship is indicated by a "yes" or "no" response to the question: Is there a reasonable possibility that the event may have been caused by talimogene laherparepvec or surgery?

The investigator must assess whether the adverse event is possibly related to any study-mandated activity and/or procedure (including any screening procedures). This relationship is indicated by a "yes" or "no" response to the question: "Is there a reasonable possibility that the event may have been caused by a study activity and/or procedure"?

The investigator is responsible for reviewing laboratory test results and determining whether an abnormal value in an individual study subject represents a clinically significant change from the subject's baseline values. In general, abnormal laboratory findings without clinical significance (based on the investigator's judgment) are not to be recorded as adverse events. However, laboratory value changes that require treatment or adjustment in current therapy are considered adverse events. Where applicable,

clinical sequelae (not the laboratory abnormality) are to be recorded as the adverse event.

The investigator is expected to follow reported adverse events until stabilization or reversibility.

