## 6. Definitions

The definitions of efficacy endpoints are given in [Section 4](#).

- Investigational Product

Investigational product refers to talimogene laherparepvec in this study.

- Study Drug

Study drug is defined as talimogene laherparepvec in this study.

- Screening Phase

The screening phase is the time period after signing the informed consent and before enrollment when study specific laboratory tests and procedures are performed, and medical history is reviewed to confirm subject eligibility for the study.

- Study Day 1

Study day 1 for a subject is defined as the first day that the study drug is administered to the subject or the surgical resection of melanoma tumor lesion(s), whichever is earlier. Study day 1 is the date of randomization if a subject does not

receive talimogene laherparepvec or the surgical resection of melanoma tumor lesion(s). The day before the study day 1 is referred to as study day -1.

- Baseline

Baseline in general refers to study day 1. The baseline value of a parameter (eg, vital signs, laboratory tests and efficacy endpoints) is considered to be the latest value prior to receiving talimogene laherparepvec or the onset of the surgical resection of melanoma tumor lesion(s), whichever is earlier. If subjects that do not receive study therapy or the surgical resection of melanoma tumor lesion(s), the baseline value will be the last record on or prior to the randomization date.

[figure not shown]
- Treatment Period (also Study Treatment Period, Overall Treatment Period)

Study day 1 through 30 days after the last administration of talimogene laherparepvec or 30 days after the surgical resection of melanoma tumor lesion(s), whichever is later.

- Talimogene Laherparepvec Monotherapy Period (Arm 1 Only)

Talimogene laherparepvec monotherapy period starts at the initiation of the first talimogene laherparepvec dose administration and ends before the surgical resection of the melanoma tumor lesion(s), or 30 days after the last administration of talimogene laherparepvec, whichever is earlier.

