## 7.2 Safety Analysis Set

The safety analysis set will include all randomized subjects who received talimogene laherparepvec or surgical resection of melanoma tumor lesion(s). The safety analyses will be performed by treatment received (i.e., neoadjuvant talimogene laherparepvec + surgical resection versus surgical resection alone). Subjects will be classified in the talimogene laherparepvec arm for safety analyses if they received at least one administration of talimogene laherparepvec at any time during the treatment period.

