## 10. Statistical Methods of Analysis

### 10.1 General Principles

All analyses will be descriptive with no formal hypothesis testing.

In principle, mean, standard deviation, median, first and third quartiles, minimum and maximum will be calculated for continuous variables; frequency and percent will be calculated for binary and categorical variables. Graphical summaries of the data may also be presented.

Analyses of tumor tissue or serum biomarkers may be performed after collection of all samples during the conduct of the study and therefore may be reported after the primary analysis of efficacy endpoint.

The primary analysis for efficacy endpoints will be performed on the Intent to Treat Analysis Set by randomized treatment. In addition, some of the analysis may be repeated on the Efficacy Analysis Set by treatment actually received. Safety analyses will be conducted on the Safety Analysis Set.

Data analysis is scheduled to occur at the following time points:

- Two interim analyses with no formal stopping rules will be performed when approximately 40 and 75 subjects randomized to talimogene laherparepvec have had the opportunity to complete the safety follow-up visit. (Please refer to [section 8.1](#) for details).
- An additional third interim analysis with no formal stopping rule is planned to evaluate RFS approximately 1 year after the end of randomization. This analysis will be conducted by the Amgen study team. (Please refer to [section 8.1](#) for details).
- The primary analyses for RFS will occur at the later time of either the occurrence of approximately 64 events (local, regional, or distant recurrence of melanoma or death) or approximately 2 years after end of randomization. The primary analysis for certain secondary endpoints (eg, response to neoadjuvant treatment, R0 resection rate, pCR rate, and safety) will be performed using the data from the second interim analysis.
- The final analyses will occur approximately 5 years after the end of randomization. An additional analysis will also occur approximately 3 years after the end of randomization.
- Ad hoc analyses for safety or some efficacy endpoints (eg, response to neoadjuvant treatment, R0 resection rate, pCR rate) may be conducted before the planned primary and/or final analyses if interim data are required for submission to regulatory authorities. These ad hoc analyses will be executed by the **Amgen study** team.

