## **10.6 Safety Analyses**

### **10.6.1 Adverse Events**

The Medical Dictionary for Regulatory Activities (MedDRA) version 19.1 or later will be used to code AEs to a system organ class (SOC) and a preferred term within the SOC. The CTCAE version 3.0 will be used to grade severity of AEs.

Only treatment-emergent adverse events (see [Section 6](#) for definition) will be summarized by treatment received. Subject incidence rates of all treatment-emergent, grade  $\geq 3$ , serious, non-serious, treatment related, serious treatment related, non-serious treatment related, events leading to talimogene laherparepvec withdrawal/delay/less than 4ml volume per administration, events leading to cancel the scheduled surgical removal of the melanoma tumor lesion(s), fatal adverse events and local effects on the lesion (i.e., pain, inflammation and ulceration) as well as adverse events of interest will be tabulated by SOC and PT in descending order of frequency within an SOC. For all treatment-emergent adverse events additional summary tables will also be provided by (1) SOC, PT in descending order of frequency within an SOC and worst CTCAE grade, and (2) PT in descending order of frequency.

In addition, certain categories of adverse events occurring within the talimogene laherparepvec monotherapy period and within the period after the start of the first dose of talimogene laherparepvec of  $10^6$  PFU/mL but before the first dose talimogene laherparepvec of  $10^8$  PFU/mL will be summarized separately by system organ class and preferred term in descending order of frequency. These categories of adverse events include all treatment-emergent adverse events, serious treatment-emergent adverse

events, non-serious treatment-emergent adverse events, talimogene laherparepvec related treatment-emergent adverse events.

Subgroups group analyses for age group (< 65, ≥ 65 and < 75, ≥ 75), sex, and race (white vs not white) will be presented for all treatment-emergent adverse events by system organ class and preferred term by treatment received in descending order of frequency.

Narratives of deaths through either the 30 days after the last dose of talimogene laherparepvec or the surgical resection of melanoma tumor lesion(s), whichever is later, will be provided.

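### The SAP's table of adverse events that cancel surgery reads zero for surgery alone by construction, apart from narrow exceptions, so that row cannot compare the arms

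*SAP*

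**What the plan says.** SAP 10.6.1 lists the adverse-event categories to be tabulated by system organ class and preferred term. One is "events leading to cancel the scheduled surgical removal of the melanoma tumor lesion(s". The counting rule for all of them is "Only treatment-emergent adverse events (see [Section 6](#) for definition) will be summarized by treatment received". SAP 10.1 fixes the population: "Safety analyses will be conducted on the Safety Analysis Set".

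SAP 7.2 sets entry to that population: "The safety analysis set will include all randomized subjects who received talimogene laherparepvec or surgical resection of melanoma tumor lesion(s". A subject is placed in the talimogene laherparepvec column "if they received at least one administration of talimogene laherparepvec at any time during the treatment period". Later surgery is not required.

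SAP Section 6 sets the clock. "Study day 1 for a subject is defined as the first day that the study drug is administered to the subject or the surgical" resection, whichever comes first. A subject with neither takes the randomization date instead. The Treatment Period runs from Study day 1 to 30 days after the last dose or the resection, whichever is later. Events with onset in that period are treatment-emergent, and events on its first or last day normally count.

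Two other provisions bear on the point. Protocol 9.2.1 requires reporting of adverse events "that occur after randomization through the safety follow-up visit", without distinction by arm. SAP 10.2 summarizes reasons for not receiving surgery by randomized treatment. SAP 10.6.7 also summarizes why surgery was not done, without stating the population or columns.

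**The concern.** The row records loss of the planned operation. In Arm 2, having that operation is the only way into the population in which the row is counted. The outcome therefore removes the Arm 2 subject from both numerator and denominator. In Arm 1 the same outcome leaves the subject in the table, because the first injection has already admitted them.

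Comparing safety between arms is a secondary objective. Arm 1 surgery falls in weeks 13 to 18 for subjects who complete treatment, against weeks 1 to 6 in Arm 2, so loss of resection to an adverse event is a natural thing to compare. A reader who turns to this row would see an Arm 1 percentage beside a surgery-alone zero, with nothing to say that the zero comes from the definitions and was not observed.

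**Working it through.** **Step 1. Apply the definitions case by case** (SAP Section 6, 7.2, 10.1, 10.6.1).

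| Subject | In Safety Analysis Set? | Event treatment-emergent? | Counted? |
|---|---|---|---|
| Arm 2, surgery cancelled and never done | No: neither dose nor resection | Study day 1 falls back to randomization and no end of period is defined; immaterial, as the subject is outside the set | No |
| Arm 2, date cancelled, operated on later, event before the day of surgery | Yes | No: Study day 1 is the day of surgery | No |
| Arm 2, event on the day of surgery, or after a first resection and cancelling a further one | Yes | Yes | Yes (narrow exceptions) |
| Arm 1, dosed, surgery never done | Yes, from first dose | Yes, up to 30 days after the last dose | Yes, unless onset is later |
| Arm 1, dosed, operated on later | Yes | Yes | Yes |

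The Arm 1 gap in the fourth line is real. Subjects who stop dosing early may have surgery up to 6 weeks, or 6 × 7 = 42 days, after the last dose. If surgery never happens, the period closes at day 30, which leaves up to 42 − 30 = 12 days uncovered.

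**Step 2. Illustrate the effect.** The plan gives no figure for this row, so there is none to reproduce. Inputs:
- 150 subjects randomized 1:1 (SAP 3.2), taken as 75 per arm.
- An assumed equal number c in each arm who never have surgery because of an adverse event.
- All Arm 1 subjects dosed, all other subjects operated on, and all Arm 1 events inside the window.

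The row as planned shows c/75 against 0/(75 − c). On all randomized subjects it would show c/75 against c/75.

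| c | Row as planned | Difference (80% CI) | All randomized: difference (80% CI) |
|---|---|---|---|
| 2 | 2/75 = 2.7% vs 0/73 = 0% | +2.7% (−1.2% to +7.1%) | 0.0% (−4.9% to +4.9%) |
| 4 | 4/75 = 5.3% vs 0/71 = 0% | +5.3% (+0.8% to +10.5%) | 0.0% (−6.0% to +6.0%) |
| 6 | 6/75 = 8.0% vs 0/69 = 0% | +8.0% (+2.9% to +13.8%) | 0.0% (−6.8% to +6.8%) |

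The intervals use the continuity-corrected Wilson score method of SAP Appendix B.4 at 80%. They only gauge scale: SAP 10.6.1 plans no interval for adverse events. For c = 4, the single-arm limits are l₁ = 0.0240 and u₁ = 0.1055 for 4/75, and l₂ = 0 and u₂ = 0.0350 for 0/71. Then:
- Lower limit = 0.0533 − √[(0.0533 − 0.0240)² + (0.0350 − 0)²] = 0.008.
- Upper limit = 0.0533 + √[(0 − 0)² + (0.1055 − 0.0533)²] = 0.105.

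**Step 3. How likely is a one-sided row?** With a true rate p per subject, the chance of at least one Arm 1 case is 1 − (1 − p)^75. This is 0.78 at p = 0.02, 0.979 at p = 0.05 and nearly 1 at p = 0.10. These rates are also assumptions.

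**The case against.** The strongest reply is that lost surgery is already compared elsewhere. SAP 10.2 gives reasons for not receiving surgery by randomized treatment, alongside counts of treated and untreated subjects. That stands, and it limits the harm. It does not repair the 10.6.1 row: the disposition summary is not specified to give an adverse-event term or grade, and it could report Arm 2 losses to adverse events while the adverse-event table reports none.

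Other parts of the reply also stand:
- All analyses are descriptive, and no test or interval is planned for this row.
- The same list in SAP 10.6.1 already contains categories that can only occur with the study drug, such as withdrawal or delay of it, so one-sided rows are not new to its readers.
- Any distortion runs against the sponsor's product, and RFS is untouched.
- Equal cancellation numbers are an assumption, since the pre-surgery interval differs between arms. The true number in Arm 2 may be none.

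Three stronger readings are tempting, and the documents do not support them. First, a reader might infer that a never-operated Arm 2 subject has no treatment-emergent window. Section 6 starts that subject's clock at randomization, so exclusion from the Safety Analysis Set is what decides the case. Second, a reader might infer that every Arm 1 cancellation after dosing is counted. Late onsets are missed, as Step 1 shows. Third, a reader might infer that the plan has no between-arm information on lost surgery. SAP 10.2 provides some.

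**Conclusion.** The point holds in a limited form. Under the SAP's own definitions, cancellation of surgery for an adverse event is countable in Arm 1, except for onsets more than 30 days after the last dose when surgery never happens. In Arm 2 it is not countable, apart from an event on the day of surgery or one that cancels a further resection. The row therefore cannot support a between-arm comparison.

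Severity is low. One descriptive safety table is affected, and the disposition summary offsets part of the loss. The conclusion about the zero rests on definitions alone. The size does not: the 2.7% to 8.0% against 0% depends on an assumed equal 2 to 6 of 75 per arm, and the actual distortion is unknown.

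**What to change.** In SAP 10.6.1, take this category out of the tables restricted to treatment-emergent events in the Safety Analysis Set. Tabulate it by randomized arm in all randomized subjects, with preferred term and worst grade. Count events with onset from randomization in both arms and, where surgery is not done, through the scheduled surgery date. This also closes the late gap in Arm 1. Footnote that the population differs from the other adverse-event tables.

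At minimum, keep the row, mark the surgery-alone column as not estimable, and refer the reader to the disposition summary in SAP 10.2.

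The cost is SAP wording, one re-specified table and a footnote. Adverse events are already reported from randomization. Two points need checking against the CRF, which is not among the documents: that cancellation of surgery can be recorded as the consequence of an event in Arm 2, and how long events are collected when surgery never takes place, since Protocol 9.2.1 ends collection relative to surgery.

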#### **10.6.2 Laboratory Test Results**

Laboratory values will be summarized descriptively. In addition, grade shifts in laboratory value from baseline to worst on-study value (according to NCI Common Toxicity Criteria (CTC) version 3.0 grading) and grade 3 or higher laboratory toxicities will be presented for selected laboratory tests with CTC grade. Textbook lower and upper limits of the normal ranges will be used for CTC grading, where applicable. For serum lactate dehydrogenase (LDH) local laboratory range will be used.

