1.2 Secondary

The secondary objectives are:

- To estimate the effect of neoadjuvant talimogene laherparepvec plus surgery compared to surgery alone on **1-year**, 2-year, 3-year, and 5-year RFS
- To estimate the effect of neoadjuvant talimogene laherparepvec plus surgery compared to surgery alone on rate of histopathological tumor-free margin (R0) surgical resection
- To estimate the effect of neoadjuvant talimogene laherparepvec on rate of pathological complete response (pCR)
- To estimate the effect of neoadjuvant talimogene laherparepvec plus surgery compared to surgery alone on local recurrence-free survival (LRFS), regional recurrence-free survival (RRFS), and distant metastases-free survival (DMFS)
- To estimate the effect of neoadjuvant talimogene laherparepvec plus surgery compared to surgery alone on **1-year**, 2-year, 3-year, 5-year, and overall survival (OS)
- To estimate response to neoadjuvant talimogene laherparepvec overall and separately in injected and uninjected lesions during treatment (Arm 1 only)
- To evaluate the safety of neoadjuvant talimogene laherparepvec plus surgery compared to surgery alone

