Informed Consent	X				
Review of Medical/Surgical History	X				
Demographic Data (sex, age or date of birth, race, and ethnicity)	X				
Review of Eligibility Criteria	X				
Concomitant Medications	X		X	X	
Adverse and Serious Adverse Events	X		X	X	
Physical Exam	X			X	
Vital Signs	X		X	X	
ECOG Performance Status	X			X	
Surgical Safety Evaluation (including wound closure, drain time, and post operation infection)				X	
Subsequent Anticancer Therapy for Melanoma				X	X
Survival					X
LOCAL LABORATORY ASSESSMENTS					
Urine or Serum Pregnancy Test		X		X	
Hematology	X			X	
Chemistry	X			X	
Serum LDH	X				
PT, PTT or aPTT, INR	X				

Footnotes defined on next page of the table

Table 3. Schedule of Assessment for Arm 2 (Surgery Alone)

	Screening ^a		Treatment Period ^b	Follow-up Period ^c	
	≤ 28 days	≤ 3 days	At time of Surgery (Week 1 to 6)	Safety Follow-up 30 (+15) days	Long-term Follow-up Every 3 months (± 30 days) for 3 years then every 6 months (± 30 days) until 5 years after randomization
CENTRAL LABORATORY ASSESSMENTS					
Archived Tumor Tissue for Biomarker Analyses			Submit to central laboratory within 28 days after randomization		
Archived Tumor Tissue for BRAF ^{V600} Mutation Testing			Submit to central laboratory within 28 days after randomization if BRAF ^{V600} mutation status is unknown prior to screening and was not tested at local laboratory		
Tumor Biopsy			X		
Blood for Biomarker Development			X		
TREATMENT					
Surgery			X		
RADIOGRAPHIC IMAGING, CLINICAL, AND HISTOLOGICAL TUMOR ASSESSMENTS					
Radiographic Imaging (CT, PET/CT, MRI)	X				X
Clinical Tumor Measurement and Response Assessment	X				X
Histological Tumor Assessment of Surgical Specimen ^d			X		

Page 2 of 2

^a For additional information regarding the procedures performed during screening procedures and the timing of the procedures please refer to [Section 7.2.1](#).

^b For additional information regarding the procedures performed during treatment and the timing of the procedures please refer to [Section 7.2.2](#).

^c For additional information regarding the procedures performed during safety follow-up and long-term follow-up and timing of the procedures please refer to [Section 7.2.3](#) and [Section 7.2.4](#), respectively.

^d Surgical specimens will be assessed for presence of viable tumor and tumor margin status for cutaneous and subcutaneous tumor; please refer to [Section 7.2.2](#).

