7.2.2 Treatment

Treatment begins when the first dose of protocol-required therapies is administered to a subject (Arm 1) or the subject undergoes surgery (Arm 2).

The following procedures will be completed during the treatment period at the times designated in the Schedule of Assessments ([Table 2](#) and [Table 3](#)).

- Vital signs (systolic/diastolic blood pressure, heart rate, respiratory rate, temperature): Subject must be in a supine position in a rested and calm state for at least 5 minutes before blood pressure assessments are conducted. If the subject is unable to be in the supine position, the subject should be in most recumbent position possible. The position selected for a subject should be the same that is used throughout the study and be documented on the vital signs CRF.
 - Arm 1: prior to talimogene laherparepvec administration on day 1 of weeks 1, 4, 8, 12, and prior to surgery
 - Arm 2: within 3 days prior to surgery
- Physical examination as per standard of care
 - Arm 1: within 3 days prior to talimogene laherparepvec administration on day 1 of week 1 and within 3 days prior to surgery, and prior to talimogene laherparepvec administration on day 1 of weeks 4 and 8
- ECOG performance status
 - Arm 1: prior to talimogene laherparepvec administration on day 1 of weeks 4 and 8 and within 3 days prior to the surgery

- Local laboratory assessments
 - Arm 1: prior to talimogene laherparepvec administration on day 1 of weeks 1, 6, 12. Screening laboratory values may be used for week 1 day 1 assessment if completed within 3 days of study treatment initiation. On treatment tests can be performed within 3 days of the planned visit. Results should be reviewed prior to the administration of study drug
 - Hematology panel: hemoglobin, hematocrit, WBC with 5-part differential (3-part differential if 5-part unable to be performed), RBC, platelet
 - Chemistry panel: sodium, potassium, chloride, calcium, magnesium, phosphorus, uric acid, total protein, albumin, BUN, creatinine, total bilirubin, alkaline phosphatase, AST, ALT, glucose
- Central laboratory assessments:
 - Blood for HSV-1 antibody serostatus
 - Arm 1: within 3 days of day 1 of week 1 (prior to administration of talimogene laherparepvec)
 - Blood for biomarker analysis
 - Arm 1: within 3 days of day 1 of week 1 (prior to administration of talimogene laherparepvec) and week 6 (prior to administration of talimogene laherparepvec) and within 3 days prior to the day of surgery

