10.5.4 Safety Endpoints

Subject incidence rates of treatment-emergent adverse events (including all adverse events, grade ≥ 3 adverse events, fatal adverse events, serious adverse events, adverse events of interest and events requiring the discontinuation of study drug, local effects on the tumor [ie, pain, inflammation and ulceration]) will be summarized. The Medical Dictionary for Regulatory Activities (MedDRA) will be used to code adverse events to a system organ class (SOC) and a preferred term within the SOC. The CTCAE version 3.0 will be used to grade severity of adverse events. In addition, clinically significant laboratory changes and clinically significant changes in vital signs will be summarized with descriptive statistics. Summary statistics will also be provided for concomitant medications, adjuvant therapy, dose delay, study drug discontinuation, overall exposure, and changes in ECOG performance status. Tables and/or narratives of deaths through 30 days after the latter of the last dose of talimogene laherparepvec or surgery will be provided. The incidence of subjects with herpetic lesions found to be positive for talimogene laherparepvec DNA per qPCR in swab samples collected from lesions suspected to be herpetic in origin and the rate of positive lesions (if any) will be calculated. Potential or known unintended exposure to talimogene laherparepvec, related suspected signs or symptoms, and detection of talimogene laherparepvec in a subject's household member, caregiver, or healthcare provider will be reported.

When appropriate, the safety data during the talimogene laherparepvec monotherapy period before surgical resection will be summarized separately from the safety data after surgical section, which will be summarized by treatment actually received.

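### Worst on-study laboratory grade draws on up to three scheduled panels in Arm 1 but one in Arm 2, so the side-by-side table is expected to look worse for Arm 1 even with no drug effect

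*SAP*

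**What the plan says.** SAP 10.6.2 first promises a descriptive summary of laboratory values. It then adds "grade shifts in laboratory value from baseline to worst on-study value" and states that "grade 3 or higher laboratory toxicities will be presented for selected laboratory tests with CTC grade". It gives no visit window, no visit matching and no split at surgery. *On-study* is not defined in SAP Section 6.

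SAP 7.2 fixes the grouping: "The safety analyses will be performed by treatment received", meaning talimogene laherparepvec plus surgery against surgery alone. The safety objective in Protocol 1.2 is comparative: "To evaluate the safety of neoadjuvant talimogene laherparepvec plus surgery compared to surgery alone".

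The sampling schedules differ. For Arm 1, Protocol 7.2.2 places the hematology and chemistry panels "prior to talimogene laherparepvec administration on day 1 of weeks 1, 6, 12". Table 2 shows the same visits plus screening and safety follow-up. For Arm 2, the block headed "LOCAL LABORATORY ASSESSMENTS" in Table 3 marks these panels at screening and safety follow-up only.

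Protocol 10.5.4 contains a possible remedy. Where appropriate, "the safety data during the talimogene laherparepvec monotherapy period before surgical resection will be summarized separately" from the post-surgery data. SAP 10.6.1 carries this out for adverse events. SAP 10.6.2 does not mention it for laboratory data.

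**The concern.** A worst value is a maximum, and a maximum over more samples tends to be larger. Each extra Arm 1 panel gives another chance to record a higher grade, and Arm 2 has no matching chance. A side-by-side table would then show an Arm 1 excess that mixes any drug effect with sampling frequency.

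The SAP recognises this kind of problem elsewhere. Section 9.4.2 says that schedule differences between arms could bias detection of recurrence, and it plans an analysis for that. Vital signs (10.6.3) and ECOG status (10.6.4) are summarized by visit, so they are not exposed in the same way. Laboratory shifts get neither protection. What is at stake is a fair reading of the comparative safety tables.

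**Working it through.** **Step 1. Count the scheduled post-baseline panels.** SAP Section 6 defines baseline as the last value before the first dose or surgery, whichever comes first. The Arm 1 week 1 panel is drawn before dosing, so it counts as baseline.

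| Tests | Arm 1 after baseline | Arm 2 after baseline |
|---|---|---|
| Hematology | week 6, week 12, safety follow-up = 3 | safety follow-up = 1 |
| 11 chemistry analytes listed in 7.2.3 (sodium, potassium, chloride, total protein, albumin, calcium, creatinine, total bilirubin, alkaline phosphatase, AST, ALT) | 3 | 1 |
| Magnesium, phosphorus, uric acid, BUN, glucose (in 7.2.2 and Table 4, not in the 7.2.3 list) | week 6, week 12 = 2 | 0 |
| LDH, coagulation | 0 | 0 |

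Three is a scheduled maximum. Subjects who stop treatment early have fewer panels, and unscheduled tests can add values in either arm.

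**Step 2. Direction.** One of the three Arm 1 panels is the same post-surgery visit that Arm 2 has. For any subject, the worst of a set that includes that panel cannot be better than that panel alone. If the drug has no effect, so that both arms have the same risk at safety follow-up, the Arm 1 worst-value rate is at least Arm 2's. It is higher as soon as some subjects have a worse grade at week 6 or 12 than at follow-up. This step needs no assumed rate.

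**Step 3. Size.** The documents give no laboratory abnormality rates and no figure to reproduce. Assume the same risk p of an abnormal result at every panel in both arms, and an exchangeable latent-normal correlation ρ between panels within a subject.

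- Arm 2, one panel: p.
- Arm 1, three panels, ρ = 0: 1 − (1 − p)³. At p = 0.05 this is 1 − 0.95³ = 0.143.
- Arm 1, ρ > 0: 1 − ∫ Φ[(t − √ρ·x)/√(1 − ρ)]³ φ(x) dx, with t = Φ⁻¹(1 − p).

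Arm 1 rate, with the ratio to Arm 2 in brackets:

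| p (Arm 2 rate) | ρ = 0 | ρ = 0.3 | ρ = 0.5 | ρ = 0.8 |
|---|---|---|---|---|
| 2% | 5.9% (2.94) | 5.5% (2.76) | 5.1% (2.55) | 4.0% (2.00) |
| 5% | 14.3% (2.85) | 13.0% (2.61) | 11.8% (2.37) | 9.3% (1.85) |
| 10% | 27.1% (2.71) | 24.2% (2.42) | 21.8% (2.18) | 17.2% (1.72) |
| 20% | 48.8% (2.44) | 43.0% (2.15) | 38.9% (1.94) | 31.3% (1.57) |

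With about 75 subjects per arm (150 randomized 1:1), p = 0.05 and ρ = 0.5 give 75 × 0.118 = 8.9 against 75 × 0.05 = 3.8 subjects. For a rare grade 3 or higher event, take p = 0.01 with independent panels: 1 − 0.99³ = 0.0297, and the excess is 75 × (0.0297 − 0.01) = 1.5 subjects.

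**Step 4. The window.** The treatment period in SAP Section 6 ends 30 days after surgery or after the last dose, whichever is later. Planned surgery follows the last dose, so surgery sets the end. The safety visit falls 30 (+15) days after surgery, on days 30 to 45. If *on-study* means the treatment period, a visit on days 31 to 45 falls outside it. Those Arm 2 subjects would then have no qualifying scheduled panel.

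**Step 5. Shared panel only.** Comparing safety follow-up with safety follow-up is p against p, for example 5.0% against 5.0%. The ratio is 1.00 when there is no drug effect.

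**The case against.** The strongest reply is that the protocol already deals with this. Section 10.5.4 speaks of safety data generally, the same section covers laboratory changes, and SAP Section 11 does not list the separate pre-surgery summary as withdrawn. That is fair as far as it goes: the SAP is silent on applying the split to laboratory data and does not reject it. But the protocol sentence is conditional, and an analyst following SAP 10.6.2 as written would produce the unbalanced table.

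A second reply is that nothing formal depends on it. The listed safety endpoint is adverse event incidence, laboratory shift is not an endpoint, and there is no hypothesis testing. This stands, and it limits the consequence to how the tables read. The descriptive summaries that come first in 10.6.2 may also help a careful reader, so it would be too much to say that the artefact could never be recognised.

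A third reply is that toxicity before surgery belongs to the Arm 1 regimen and should be visible. Agreed. It should be shown, but not set against an arm that was not sampled in that period.

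A reader might also infer that the SAP plans an LDH shift that cannot be produced. The documents do not support this. Section 10.6.2 names only the reference range to use for LDH, and the shift table covers unspecified selected tests. The most that can be said is that no post-baseline LDH is scheduled.

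**Conclusion.** The point holds for hematology and the 11 chemistry analytes in Protocol 7.2.3: up to three scheduled post-baseline panels in Arm 1 against one in Arm 2. For the other five chemistry analytes the schedule is two against none, so there is no scheduled comparison at all. The direction of the bias, against Arm 1, follows from the schedules.

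The size does not follow from the documents. The ratio of about 1.6 to 2.9 rests on an assumed per-panel risk of 0.02 to 0.20, equal before and after surgery and in both arms, and on an assumed correlation of 0 to 0.8. It would reach 1 only if panels were perfectly correlated within a subject. For rare high-grade events the absolute excess could be one or two subjects.

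A reader might take the ratios as a forecast that talimogene laherparepvec will appear two to three times as toxic, or conclude that the safety evaluation is invalid. Neither is supported. The ratios illustrate a mechanism under assumed inputs, three panels is a maximum, and every analysis is descriptive. This is a worthwhile and inexpensive improvement to the tables, not a flaw in a formal comparison.

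**What to change.** In SAP 10.6.2:

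1. Define *on-study* for laboratory data so that the 30 (+15) day safety follow-up panel is included. This must come first, because the comparison below depends on that panel.
2. Make the between-arm shift table and the grade 3 or higher table on that shared post-surgery panel, for hematology and the 11 chemistry analytes listed in Protocol 7.2.3.
3. Report the worst value over the talimogene laherparepvec monotherapy period (weeks 6 and 12) as an Arm 1-only table, in line with Protocol 10.5.4.
4. Show magnesium, phosphorus, uric acid, BUN and glucose for Arm 1 only, or reconcile the 7.2.3 list with Table 4.
5. If an overall worst on-study table is kept, footnote the number of scheduled panels per arm.

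The cost is SAP wording and re-cut tables, with no new samples. The downside is real: the between-arm table would no longer include on-treatment values. With surgery planned at least a week after the last dose and the visit at least 30 days after surgery, the shared panel comes more than a month after dosing and may miss transient effects. Those would appear only in the Arm 1 table, without a control.
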